2.4.3 Considerations regarding brentuximab vedotin, CD30, and HIV

CD30 has also been studied in HIV replication, in addition to lymphoma. In fact, increased levels of the soluble form of CD30, sCD30, are predictors of progression to AIDS⁴⁴⁻⁴⁷. Levels of sCD30 also have been shown to correlate with HIV viremia levels and clinical outcome in patients with primary HIV infection in the pre-HAART era⁴⁷. Furthermore, CD30 stimulation directly induces HIV expression through activation of the transcription factor NF-kB⁴⁵⁻⁴⁷. In addition, CD30/CD30L interactions lead to virus production also in primary CD4+ T cells from HIV-positive patients⁴⁷. Both agonistic anti-CD30 antibodies and CD30L-expressing, glutaraldehyde-fixed CD8+ human T cell clones significantly enhanced HIV expression in human CD4+ T cells obtained from HIV-infected individuals⁴⁴⁻⁴⁷. This data suggests that the activation of CD30 expression in HIV-infected CD4+ T cells may allow the interaction of these cells with CD30L-expressing cells and, therefore, favor HIV replication⁴⁴⁻⁴⁷. The result of the use of the brentuximab vedotin and its effects on HIV replication will be monitored closely in this study. All participants on study must be on concurrent HAART therapy. We will test for

a multiplexed inflammatory marker panel that includes sCD30, as well as several other molecules (several soluble cytokine receptors and BAFF/BLyS and CXCL13 (BLC/BCA-1) for changes with the use of brentuximab vedotin and correlate this with changes in HIV viral load as well as clinical outcome. See Section 2.6 for a description of all correlative studies.

2.4.4 Considerations regarding progressive multifocal leukoencephalopathy associated with HIV, brentuximab vedotin, and HIV-cHL

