- 8.2.7 CD4/CD8 count will be performed within 48 hours of cycle 2 and cycle 5 day 1 along with the CBC evaluation.
- 8.2.8 HIV-1 RNA viral load, to be assessed by any FDA-approved viral load assay (evaluated at the local laboratory). This will be performed within 48 hours of cycle 2 and cycle 5 day 1 along with the CBC evaluation. (The HIV viral load assay must detect at minimum viremia >200 copies/mL to be consistent with the DHHS HIV treatment guidelines).

For participants with undetectable HIV viral at baseline: If the viral load rises above 200 copies per mL, HIV resistance testing will be required. Both viral load and resistance testing information must be shared in real time with the primary HIV provider if different from the protocol investigator. (The HIV viral load assay must detect at minimum viremia >200 copies/mL to be consistent with the DHHS HIV treatment guidelines).

- 8.2.9 Serum or urine pregnancy test for women of childbearing potential will be performed per institutional guidelines during the study.
- 8.2.10 Plasma samples to be taken for EBV tumor DNA studies at the end of cycles 1 and
 3. See Section 10.0 and Appendix XI for time points needed, sample processing, and shipping instructions. This will be done only in the Phase II portion of the study.
- 8.2.11 Plasma samples to be taken for cytokine studies. See Section 10.0 and Appendix X for time points needed, sample processing, and shipping instructions. This will be done only in the Phase II portion of the study.
- 8.2.12 Pharmacokinetic/Immunogenicity studies in select Phase II participants only. See Appendix IX for details on time points, sample processing, and shipping.
- 8.2.13 Blood samples will be taken for analysis of latent and HIV reservoirs. See Section 10.0 and Appendix XII for time points needed, sample processing, and shipping instructions.

8.3 **Post Treatment Evaluation**

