The studies listed below will be performed post-therapy within 6-8 weeks of the last treatment dose (6-8 weeks after Cycle 6 Day 15; all follow up time points for post-treatment evaluations should be calculated in reference to this treatment discontinuation visit). Studies will then be repeated every 3 months (+/- 7 days) thereafter for 2 years; every 6 months (+/- 7 days) for the third through the fifth years unless otherwise specified. All study participants should be followed for up to 5 years after treatment discontinuation or until death if occurring before 5 years of treatment discontinuation. Participants who discontinue all protocol therapy after a CR or PR are followed for up to 5 years after treatment for recurrence and survival. Participants who discontinue protocol therapy due

to disease progression or other reasons are followed for survival for up to 5 years after treatment discontinuation. No additional studies except follow up for survival are required after disease progression. In those instances in which a third party payer denies payment for some or all of these laboratory analyses, absence of these test results will not be considered a protocol violation.

- 8.3.1 Medical history.
- 8.3.2 Physical examination, including performance status (see Appendix III, Performance Status Scale), vital signs (weight, height, body surface area), neurological examination, and if possible, two dimensional measurement of all palpable, peripheral lymph nodes and measurement of other sites of disease present on physical exam.
- 8.3.3 At the conclusion of chemotherapy, a full body FDG-PET/CT scan will be done between 6-8 weeks post the final treatment dose, Cycle 6 Day 15. This will be the final FDG-PET/CT needed for the study. A combined FDG-PET/CT or FDG-PET + CT scans with and without IV contrast are required for the post-treatment scan. If a participant has an allergy to IV contrast, a CT scan without contrast will be permitted. As the false positive rate of FDG-PET scans may be higher in the HIV population, a biopsy of an unexpected FDG-PET avid lesion is recommended but remains at the discretion of the investigator.
- 8.3.4 CT scan with oral/IV contrast every 6 months for 5 years. To begin 6 months from the post treatment FDG-PET/CT scan, obtained 6-8 weeks post the final chemotherapy dose (See Section 8.3.3).

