11.2 Sample Size/Accrual Rate

No formal statistical hypothesis testing is planned for the primary analysis of the Phase I portion of the study. In the Phase II portion of the study, 51 participants will be enrolled to estimate the 2-year progression free survival. Sample size calculation is based on providing an estimate of the PFS with a 95% confidence interval $\pm 10\%$ under the hypothesis that 2-year PFS is 85%.

If there are no DLTs in the Phase 1 portion of the study, and if 100% of the Phase 1 participants are treated identically to those in the Phase 2, data from the Phase 1 and 2 portions can be combined to complete the phase 2 portion of the study.

The primary endpoint of the phase II portion will be to estimate the two-year progressionfree survival for AVD-brentuximab vedotin which will be done using Kaplan-Meier estimates and corresponding 95% confidence intervals based on standard errors using Greenwood's formula.

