11.4 Analysis of Secondary Endpoints

Descriptive summaries and exploratory analyses for secondary objectives will be conducted. Significance for comparisons will be at the p<0.05 level.

Secondary objectives include:

1. To evaluate toxicity of AVD and brentuximab vedotin with HAART.

- 2. To estimate the partial response rate, complete response rate, overall survival (OS), event free survival at 2 and 5 years. To evaluate effect of AVD and brentuximab vedotin on CD4 and CD8 counts after 2 cycles, 6 cycles, and every 3 months after treatment completion for one year.
- 3. To evaluate effect of AVD and brentuximab vedotin on viral load after 2 cycles, 6 cycles, and every 3 months after treatment completion for one year
- 4. To investigate the prognostic value of FDG-PET scans at baseline and after 2 cycles in participant with HIV and HL with respect to 2 year progression free survival.
- 5. To evaluate HAART status at baseline for difference in outcome.
- 6. The characterization of histologic subtypes in HIV-HL in the HAART era.
- 7. To assess additional neurotoxicity in combination with HAART and AVD and brentuximab vedotin.

The frequency of AEs and their severity will be tabulated to evaluate tolerance of AVD and brentuximab vedotin with HAART. Further, binomial probabilities and their 95% confidence intervals will be used to estimate the response rates (i.e., partial response rate, complete response rate, overall response rate) and event free survival at 2 and 5 years of AVD and brentuximab vedotin for a treatment of participants with stage III/IV HIV-associated Hodgkin Lymphoma.

Repeated measures analysis of variance (ANOVA) models will be used to evaluate the effect of AVD and brentuximab vedotin on CD4 counts, CD8 counts and viral load after 1, 4, and 6 cycles, and every 3 months after treatment completion for one year.

Log-rank analysis will be used to investigate the prognostic value of FDG-PET scans at baseline, after 2 cycles and post-therapy in participants with HIV and HL with respect to progression free survival.

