 - Also, if the elevated bilirubin is thought to be secondary to cHL the same criteria for hyperbilirubinemia should be applied however 1 prior cycle of cyclophosphamide is permitted in attempt to make the participant eligible (see section 8.1.5). Patients should not be excluded from study participation unless

dosing cannot be safely established per Section 10.6.2.

- 10. Female subjects must have a negative pregnancy test within 1 week of enrollment and all subjects must agree to use two reliable methods of contraception simultaneously if conception is possible during the study.
 - a. Should a woman subject become pregnant or suspect she is pregnant while the subject is participating in this study, she should inform her treating physician immediately. The patient will then be removed from protocol therapy.
 - b. Subjects who father a child while participating in the study will be permitted to continue with the protocol. The subject, however, is required to notify the investigator if he fathers a child.
- 11. Ability to understand and the willingness to sign a written informed consent document.
- 12. Karnofsky performance status > 30% (given the aggressiveness of this disease and the often severely debilitated nature of the patients at initial presentation). See Appendix 20.5.
- 13. Measurable or non-measurable (evaluable) tumor parameter(s). Non-measurable tumor parameters will be defined as not having bi-dimensional measurements (i.e., gastric or marrow involvement) but can be followed for response by other diagnostic tests such as gallium, PET imaging and/or bone marrow biopsy.
- 14. Patients already receiving erythropoietin or GCSF for treatment of HIV-related cytopenia are eligible.
- 15. CD4 count \geq 100 cells/µl and serum HIV viral load <50copies/ml

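### A pooled repeated-measures ANOVA, with no detection-limit rule and no rebound endpoint, is poorly suited to showing whether suppressed participants lose HIV control

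*Combined protocol and SAP*

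**What the plan says.** **Model.** AMC protocol Section 11.4 states: "Repeated measures analysis of variance (ANOVA) models will be used to evaluate the effect" of the regimen on CD4, CD8 and viral load during treatment and for a year afterwards. French protocol Section 16.4 repeats this. Section 11.4 adds "Descriptive summaries and exploratory analyses for secondary objectives will be conducted" and "Significance for comparisons will be at the p<0.05 level". French Section 16.0 says the French and US data are analysed together.

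**Entry.** French Section 8.1 requires "serum HIV viral load <50copies/ml". AMC Section 3.1.16 requires at least 7 days of HAART, and Section 3.1 sets no viral-load ceiling.

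**Assay.** AMC Section 8.2.8 allows local assays subject to a minimum: "The HIV viral load assay must detect at minimum viremia >200 copies/mL". For participants undetectable at baseline, a later value above 200 copies/mL triggers resistance testing.

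**Follow-up.** AMC Section 8.3 states: "No additional studies except follow up for survival are required after disease progression". Under Section 8.4, early discontinuation brings one further CD4, CD8 and viral-load sample within a month, then survival follow-up only.

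**Purpose.** Section 2.4.3 sets out laboratory evidence that CD30 stimulation induces HIV expression. Of the drug it says "its effects on HIV replication will be monitored closely in this study".

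**The concern.** The two halves of the cohort move in opposite directions. A participant at or below the assay floor can show change only by rising. A participant who recently started or switched HAART is expected to fall. A test of the pooled mean over time mixes the two. It can be significant because HAART is working, and it can show a net fall while some suppressed participants lose control.

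The result would also depend on choices the plan leaves open: raw or log10 copies, what value stands in for an undetectable result, and how differing local limits are reconciled.

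No other planned analysis clearly fills the gap. AMC Section 6.3.4.2 keeps viral load out of adverse events. The 200 copies/mL rule prompts a laboratory test and is not an endpoint. The reservoir study (Appendix XII) starts only with undetectable participants, requires undetectable plasma RNA again for its post-treatment samples, and does not apply in France. A rebound signal could be in the data and never be tabulated.

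**Working it through.** **1. The plan's own figure.** Section 11.2 says "51 participants will be enrolled to estimate the 2-year progression free survival", with a 95% interval of ±10 points at 85%. By the Wald formula, n = 1.96² × 0.85 × 0.15 / 0.10² = 48.98, so 49. At n = 51 the half-width is 9.8 points, so the stated size reproduces. No size or power is given for viral load.

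**2. How mixed the cohort is.** Guaranteed below 50 copies/mL at baseline: 20/51 = 39.2%. Not guaranteed: 31/51 = 60.8%. If a share s of those 31 is also suppressed, the overall share is (20 + 31s)/51:

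| s | overall suppressed |
|---|---|
| 25% | 54% |
| 50% | 70% |
| 75% | 85% |

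**3. A mean that falls during rebound (assumed values).** At baseline, 43 participants are set to 50 copies and 8 are at 30,000. Later the 8 are suppressed and 6 of the 43 are at 1,000.
- Baseline mean log10: (43 × log10 50 + 8 × log10 30,000)/51 = 2.135.
- Later mean log10: (45 × log10 50 + 6 × log10 1,000)/51 = 1.852.
- Rebound among the suppressed: 6/43 = 14%, exact 95% CI 5.3% to 27.9%.

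**4. Behaviour of the test (simulation, assumed values).** Settings were 51 participants, 8 visits and log10 values floored at 50 copies. Rebounds averaged 3.5 log10 over two visits. Unsuppressed participants started at a mean of 3.5 log10 and declined on HAART. A complete-case ANOVA with Greenhouse-Geisser correction was run on participants still progression-free.

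| AMC participants suppressed | true rebound | ANOVA rejects | mean change, log10 |
|---|---|---|---|
| 100% | 5% | 2% | +0.05 |
| 100% | 10% | 17% | +0.10 |
| 100% | 20% | 73% | +0.20 |
| 75% | 20% | 84% | −0.02 |
| 50% | 0% | over 99% | −0.36 |
| 50% | 20% | over 99% | −0.22 |

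With everyone suppressed, the test has little power at uncommon rebound rates. With half the AMC participants unsuppressed, it rejects almost always, with or without rebound, and the mean falls either way.

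**5. Loss to progression.** Cycle 6 Day 15 falls 154 days after the first dose. Adding 6 to 8 weeks and then 12 months puts the last viral-load visit at about 18.4 to 18.9 months. With exponential PFS through 85% at 24 months, 0.85^(18.4/24) = 0.883 and 0.85^(18.9/24) = 0.880, so about 45 of 51 remain and 12% are lost. By the end-of-treatment visit the loss is under 5%. If 2-year PFS were 75%, about 80% (41 of 51) would remain at the last visit.

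**6. What the replacement would deliver.** Exact 95% intervals: 0/51 gives 0 to 7.0%; 3/51 gives 1.2% to 16.2%; 5/51 gives 3.3% to 21.4%. If only the 20 French participants were suppressed, 0/20 gives 0 to 16.8%. With 51 suppressed and a true rate of 5%, the chance of seeing at least one rebound is 1 − 0.95⁵¹ = 93%.

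**The case against.** The written objective is the effect on viral load; rebound is inferred from the background section. The analyses are labelled exploratory, descriptive summaries are promised, and individual rises above 200 copies/mL are already acted on in real time. All of that stands. It limits the seriousness of the point, but it does not supply a prespecified rebound summary.

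A reader might also infer more than the documents support:

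- **That most values are below detection.** This is guaranteed only for the 20 French participants. A baseline majority needs 6 of the other 31 to be suppressed, which is plausible but nowhere stated. The 200 copies/mL text is a minimum assay capability, and Appendix XII gives the usual commercial limit as 50.
- **That anyone missing a visit is dropped.** The text says ANOVA models, without saying classical or complete-case. Eight visits each missed independently by 5 to 10% would leave 66% to 43% complete (0.95⁸, 0.90⁸), but the documents give no such miss rate.
- **That sampling stops at early discontinuation.** One further sample is due within a month.
- **That the trial cannot detect rebound.** The limitation lies in the model; the data collected would support a rebound proportion.

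**Conclusion.** The point holds as a weakness in the analysis choice. The only named viral-load model averages over a cohort whose two parts are expected to move in opposite directions. It has no scale, detection-limit rule or rebound endpoint, so it is poorly matched to the concern in Section 2.4.3.

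What is documented is the mixture: 20 of 51 suppressed by rule, and the rest with no ceiling. That the mean can fall during rebound follows from the mixture, but the sizes shown (2.14 to 1.85, and the simulated rejection rates) rest on assumed values. Loss to progression is modest, about 12% by the last visit under the plan's own PFS assumption. Early discontinuation adds an amount the documents do not quantify. A complete-case ANOVA, if that is what is run, would discard these participants.

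Neither the ANOVA nor its replacement can show that the regimen causes rebound, because there is no control arm. The primary endpoint is unaffected.

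**What to change.** Amend Sections 11.4 and 16.4 as follows.

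- **Main viral-load analysis.** Among participants below 200 copies/mL at baseline, report the proportion with any on-study value above 200 copies/mL, with an exact 95% CI and the number assessed. The 200 threshold is already in Section 8.2.8 and is the level every permitted assay must cover, so differing local limits matter less. Since single values count, state that this is any recorded value and not confirmed rebound.
- **Participants unsuppressed at baseline.** Report them separately, as the proportion below 200 copies/mL at each visit with exact CIs.
- **No paired test against baseline and no GEE including baseline.** Among participants selected as suppressed, the baseline proportion above 200 is zero by construction, so change can go only one way. GEE would also need a stronger missing-data assumption than a mixed model.
- **Sensitivity.** A mixed model on log10 viral load that treats undetectable values as left-censored at each assay's limit.
- **CD4 and CD8.** A mixed model for repeated measures on all available visits including baseline, with the missing-data assumption stated.

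The cost is SAP wording and a little more analysis work, with no new data or visits. Visit-wise proportions still rest on those who attend, so the number assessed must accompany each one. This is a cheap improvement.

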- 2. Appearance of any new lesion more than 1.5 cm in any axis during or at the end of therapy, even if other lesions are decreasing in size. Increased FDG uptake in a previously unaffected site should only be considered relapsed or progressive disease after confirmation with other modalities. In participants with no prior history of pulmonary lymphoma, new lung nodules identified by CT are mostly benign. Thus, a therapeutic decision should not be made solely on the basis of the PET without histologic confirmation.
- 3. At least a 50% increase from nadir in the SPD of any previously involved nodes, or in a single involved node, or the size of other lesions (e.g., splenic or hepatic nodules). To be considered progressive disease, a lymph node with a diameter of the short axis of less than 1.0 cm must increase by 50% and to a size of 1.5 x 1.5 cm or more than 1.5 cm in the long axis. At least a 50% increase in the long est.

diameter of any single previously identified node more than 1 cm in its short axis. Lesions should be PET positive if observed in a typical FDG-avid lymphoma or the lesion was PET positive before therapy unless the lesion is too small to be detected with current PET systems (< 1.5 cm in its long axis by CT).

Recurrent Disease is defined as the appearance of tumor following documentation of a complete remission.

*Time to Response* is defined as time from the first dose of chemotherapy until documentation of first response.

*Time to Progression* is defined as time from initiation of chemotherapy to documentation of first progression.

Response Duration is defined as the time from first documentation of response to documentation of first progression.

Safety Measures

All AE will be monitored by ongoing review of reported adverse events by the protocol chair and the AMC Operations and Data Management Center, and will be discussed during the monthly investigators' Lymphoma Working Group conference calls (see Section 4.7 for rules for early study termination).

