After cycle 2 and post-therapy, progression-free survival will be estimated for participants whose FDG-PET findings were negative and those whose findings were positive using Kaplan-Meier estimates and corresponding 95% confidence intervals based on standard errors using Greenwood's formula. Positive predictive value after 2 cycles and post-therapy will be estimated as the proportion of PET-positive participants who progress or die before two years; negative predictive value after 2 cycles and post-therapy will be estimated as the proportion of PET-negative participants who are progression-free and alive at two years. Sensitivity of FDG-PET at cycle 2 and post-therapy will be estimated as the proportion of participants who progressed or died prior to year 2 whose FDG-PET was positive. Specificity of FDG-PET at cycle 2 and post-therapy will be estimated as the proportion of participants who are alive and progress-free at 2 years whose FDG-PET was positive. Exact two-sided 95% confidence intervals will be used for all estimates.

Log-rank analysis will be used to evaluate HAART status at baseline for difference in outcome in terms of overall survival and progression free survival. The frequency and proportion of different histologic subtypes will be calculated.

The frequency of neurotoxicity in participants taking AVD and brentuximab vedotin in combination with/without HAART will be tabulated. A binomial test of proportions will be used to test the difference in additional toxicity between those participants taking AVD

and brentuximab vedotin on HAART vs. those participants not on HAART.

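### The cycle 2 and post-therapy PET analyses count progressions found at the same PET/CT that sets the PET group, so PET can look prognostic without predicting later failure

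*Combined protocol and SAP*

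**What the plan says.** Section 11.4 of the AMC protocol plans three things for PET. The test: "Log-rank analysis will be used to investigate the prognostic value of FDG-PET scans at baseline, after 2 cycles and post-therapy". The curves: "After cycle 2 and post-therapy, progression-free survival will be estimated for participants whose FDG-PET findings were negative", and likewise for the PET-positive group. The accuracy measures: positive predictive value is "the proportion of PET-positive participants who progress or die before two years", and "Sensitivity of FDG-PET at cycle 2 and post-therapy will be estimated as the proportion of participants who progressed or died prior to year 2" whose scan was positive. Comparisons are judged at a stated level: "Significance for comparisons will be at the p<0.05 level". Section 16.4 of the French protocol has the same text, and its Section 16.0 says that the data are pooled.

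Neither protocol states a landmark, or says what to do with a progression discovered at the scan that puts the participant in a PET group. PFS itself is never defined, neither its events nor its time origin. The nearest definition, in Section 9.2, is for Time to Progression, which "is defined as time from initiation of chemotherapy to documentation of first progression".

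Four other places bear on the point:
- Section 9.1 assesses response by the FDG-PET/CT after cycle 2 and the one after therapy, which are the scans used for grouping.
- Section 9.2, on progression, says: "Lesions should be PET positive if observed in a typical FDG-avid lymphoma". It makes an exception for lesions too small for PET to detect.
- Section 2.4.6 describes Deauville 5, the top score, as new disease.
- Section 4.6.8 (French 13.1, item 9) calls progression at cycle 2 on CT criteria alone.

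**The concern.** Section 2.6 gives the purpose of interim PET here: to validate it in HIV-associated disease, so that patients who might benefit from intensified chemotherapy can be identified. That requires a scan result that predicts failure after the scan.

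A participant whose progression is found at the scan has already failed. The progressing lesion will usually be avid, so the participant enters the PET-positive group with an event at the moment of classification. The log-rank test, the positive predictive value and the sensitivity all credit PET with that event. With few events in total, two or three such cases could produce a significant PET effect, and a respectable predictive value, from a scan that carries no information about the future.

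**Working it through.** **Inputs from the documents.** N = 51, assumed 2-year PFS 85% and a 95% interval of ±10 points (Section 11.2); significance at 0.05, taken as two-sided (11.4). The interim scan is on Cycle 2 Day 22–28 (8.2.3), about 2 months after start. The post-therapy scan is 6–8 weeks after Cycle 6 Day 15 (8.3.3). Day 15 of cycle 6 falls 5 × 28 + 14 = 154 days after start; adding 42–56 days gives 196–210 days, or 6.4–6.9 months.

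**The plan's own figure.** n = 1.96² × 0.85 × 0.15 / 0.10² = 48.98, so 49. The planned 51 gives a half-width of 9.8 points and is consistent with this. Expected events by two years: 51 × 0.15 = 7.65, about 8.

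**Inputs not in the documents.** k, the number of progressions found at the scan (all taken as PET-positive), and the PET-positive share among everyone else.

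**Log-rank simulation.** Everyone except the k has the same later risk whatever the PET result, so PET predicts nothing. There is no censoring before 24 months. With 8 events, and each other participant PET-positive with probability 15–25%, the test is significant in about:
- 5% of trials with k = 0
- 9–15% with k = 1
- 20–34% with k = 2
- 38–65% with k = 3

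Excluding the k cases returns the rate to about 4–5%.

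A second set of runs (3,000 per cell) fixed the number PET-positive among the rest, kept overall 2-year PFS at 85% and widened the share. At the cycle 2 scan:

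| PET-positive share of the rest | k = 0 | k = 1 | k = 2 | k = 3 |
|---|---|---|---|---|
| 10% | 5.2% | 19.1% | 52.6% | 85.0% |
| 20% | 3.9% | 11.3% | 26.7% | 44.0% |
| 30% | 4.3% | 9.0% | 14.5% | 31.4% |

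The post-therapy scan gave nearly the same rates. Excluding same-scan progressions brought every cell to about 4–7%. Moving time zero to the scan while keeping those progressions left every rejection rate identical.

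**Accuracy measures, k = 3 and share 20%.** The other 48 participants carry 7.65 − 3 = 4.65 events, a later risk of 4.65/48 = 9.7% in both PET groups. Ten of the 48 are PET-positive.
- Positive predictive value: (3 + 10 × 0.0969)/(3 + 10) = 3.97/13 = 30.5%, against a true later risk of 9.7%.
- Negative predictive value: 1 − 0.097 = 90.3%.
- Sensitivity: 3.97/7.65 = 52%. With k = 0 it is 10 × 0.15/7.65 = 20%.

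**What the time origin does change.** On a treatment-start clock, two years leaves about 24 − 6.7 = 17 months after the post-therapy scan. The absolute PFS and predictive values for that scan then cover 17 months of risk.

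**The case against.** A reader might infer that the clock runs from treatment start and that guaranteed event-free time creates the association. The documents do not support this. PFS has no stated origin: Time to Progression is a different endpoint, Response Duration in the same section starts at first response, and the wording in 11.4 could be read as time from the scan. The origin is not the cause in any case. Everyone classified by a scan has reached it, so time before the scan is common to both groups.

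A reader might also infer that same-scan progressions are PET-positive by construction. That is too strong. Cycle 2 progression is called on CT alone, Section 9.2 has its small-lesion exception, and it requires new uptake to be confirmed by other modalities. What remains is a strong expected overlap, since the CT belongs to the same restaging session.

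The size rests on an assumed k. The nearest figure is in Section 2.3: 2 of 62 participants had resistant disease on ABVD. If that carried over to this different regimen, 51 × 2/62 = 1.6 would be expected, before dividing them between two scans. With a Poisson mean of 1.645, three or more has probability of about 23% even if all fall at one scan. This objection stands: k = 3 is not the expected case.

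For the post-therapy scan, earlier progressors normally have no scan, because they leave treatment and the early-discontinuation visit (8.4, Appendix I) includes no PET. The simulation puts all 51 participants in that set, so it is only approximate there. Progressions first found at that scan remain at issue.

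Finally, Section 11.4 calls these analyses exploratory, and the objective asks about 2-year PFS, which the stated predictive values answer literally. That limits the severity. It does not make the stated rule suited to the aim in Section 2.6.

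**Conclusion.** The point holds for the cycle 2 and post-therapy PET analyses in both protocols. Read as written, they count progressions found at the classifying scan, and this alone can make PET look prognostic. With about 8 events and an assumed PET-positive share of 15–25%, the false-positive rate rises from about 5% to 9–15%, 20–34% and 38–65% with one, two and three such cases. The number of cases and the share are assumptions; if no progression is found at the scan, there is no bias. The cause is the counting rule and not the time origin, which affects only the absolute figures. The baseline PET analysis and the primary PFS estimate are not touched. Severity is minor: a cheap improvement to an exploratory secondary analysis.

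**What to change.** In AMC 11.4 and French 16.4:
- Define PFS, with its events and time origin.
- For the cycle 2 and post-therapy scans, set a landmark at the scan. Include participants who had that scan and were alive and not progressed on or before that assessment.
- Compute Kaplan-Meier, log-rank, predictive values, sensitivity and specificity on that set. This also settles the post-therapy sensitivity denominator, which as worded takes in people who never had the scan.
- State whether the two-year horizon runs from the scan or from treatment start.
- Report same-scan progressions separately. The all-events version can stay as a descriptive supplement.

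The cost is wording only, with no new data or participants. The price is fewer events in an already small analysis: at k = 3, about 5 of 8 remain.
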